### **7.3.3. Handling of Early Termination Visit Information**

In the event that a subject is terminated early from this study, the early termination visit data for safety variables will be assigned to the closest scheduled visit. If the closest visit has valid data, the early termination data will be assigned to the next available visit.

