Screening/Washout Visits	
Subjects with an ophthalmic history of increased IOP (≥ 22mmHg and ≤ 30 mmHg) will be selected for study participation and be screened for study eligibility.
 
After Screening, eligible subjects, if currently being treated with glaucoma medications, will be required to washout and refrain from administration of any glaucoma drugs for at least 28 days and no more than 35 days prior to the Qualification Visit. The washout subjects will be brought back at approximately two weeks after starting the washout period for an IOP safety check. In the judgement of the investigator, if there is any risk to the eye(s) of the subject, or if the mean IOP in either eye during washout is >30mmHg, then an appropriate rescue or prior medication will be administered, and the subject will be considered a screen failure. Adverse events occurring during the washout period will also be assessed at this visit.
 
Subjects not previously treated with any glaucoma drugs will not require a washout period and may return the following day or up to 35 days later for their Qualification/Baseline Visit.

Qualification/Baseline Visit	
After the washout, where applicable, a Qualification Visit will occur before dosing on Day 1.
 
At the Qualification Visit, IOP eligibility will be determined with [REDACTED] at 8AM, 10AM, and 4PM (mean IOP at 8AM must be ≥ 22mmHg and ≤ 30mmHg, and ≥ 19 mmHg at 10AM and 4PM). IOP will be measured twice in both eyes at each timepoint and the mean value will be used in eligibility assessments. All IOP measurements have a window of ± 15 minutes with at least 2 hours between the 8AM and 10AM assessments.
 
The eye with the higher IOP at the Qualification Visit at 8AM is designated as the study eye for the primary endpoint efficacy analysis. In the case where both eyes have the same IOP, the study eye will be the RIGHT eye. ALL TREATMENTS WILL BE ADMINISTERED TO BOTH EYES (OU).
 
If the subject meets all eligibility criteria, then the Qualification Visit is the Baseline Visit. The subject will then be randomized into the study.
 
The first dose of study medication will be taken at 8PM to 10PM on the Baseline Visit (Day 1).

Treatment-study Visits	
Treatment-study visits will occur twice - on Day 8 ± 1 Day and Day 15 ± 1 Day. IOP evaluations will be performed at 8AM,

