6.1. Treatment adherence

All subjects will be instructed on the importance of following the once-a-day dosing regimen. Beginning the day of the Baseline Visit (Day 1) subjects will instill one drop of study medication in each eye at 8PM to 10PM and repeat this procedure 13 times for a total of 14 doses. Subjects are to bring unused bottles into the study site on the Day 8 Visit and the Day 15 Visit. Treatment adherence will be measured by counting the dropper bottles at the start of the study, and those remaining at each study visit.

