7.2.9. Visit variation

Visits on Day 8 and 15 may be 1 day early or late. If the visit is late, the subject should be advised to take an additional dose from one of the 2 spare dropper bottles provided in the study medication box the night before the visit. The subject should then empty the remaining contents and store the opened bottle in the baggie provided and place it in the medication box for return to the study site at their next visit. If the Day 15 Visit occurs one day early or late, the Day 16 Visit and the Day 22 telephone call should be adjusted accordingly.

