##### **7.3.2. Missing Data**

The primary efficacy endpoint is the change from Baseline to Day 15 in mean diurnal IOP. For the analysis of the primary efficacy endpoint, observed case data will be used (no imputation will be performed for missing efficacy data) for the analysis using the FAS. However, confirmatory analyses will be performed using the AR population, with imputation performed for missing data as specified in [Section 7.3.2.3](#).

Otherwise there will be no substitutions made to accommodate missing data points for efficacy data. All data recorded on the case report form will be included in data listings that will accompany the clinical study report.

Safety data will be imputed in limited situations. If the severity of an AE is missing, then the severity will remain missing. If relationship of the AE to study drug is missing, the relationship will remain missing. Missing or partial dates for AEs or concomitant medications will be imputed as described in [Section 7.3.2.1](#). Otherwise, all summaries of safety endpoints will be completed using observed cases in the Safety population; no imputation will be completed.

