## **10. SAFETY ANALYSES**

All Safety analyses will be conducted using the Safety population. All safety analyses will be completed using the actual treatment a subject received. Observed case data will be used; no imputation will be performed for missing safety data except for the limited situations described in [Section 7.3.2](#).

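### SAP 7.3.3 sets no limit on the gap when it reassigns early-termination safety data, so some exit examinations would be tabulated under a visit 4 to 6 days later

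*SAP*

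**What the plan says.** SAP 7.3.3 has two steps. First, "the early termination visit data for safety variables will be assigned to the closest scheduled visit". Second, "If the closest visit has valid data, the early termination data will be assigned to the next available visit". Neither step limits the distance between the examination and the visit it is assigned to, and there is no separate label for exit data.

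The protocol's study summary fixes the on-treatment visits: "Treatment-study visits will occur twice - on Day 8 ± 1 Day and Day 15 ± 1 Day". Protocol 7.2.9 repeats the tolerance: "Visits on Day 8 and 15 may be 1 day early or late". A clinic visit on Day 16 and a phone call on Day 22 follow.

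Three other rules bear on the same data:

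- SAP 7.3.2 says that, apart from stated exceptions such as partial dates, "all summaries of safety endpoints will be completed using observed cases in the Safety population; no imputation will be completed". SAP 10 repeats that "no imputation will be performed for missing safety data except for the limited situations described in" Section 7.3.2. Section 7.3.3 is not named as an exception.
- SAP 7.3.1 keeps data from unscheduled visits out of the efficacy and safety analyses and only lists them. SAP 10.3 and 10.4 say the same for examinations and vital signs.
- Protocol 7.2.8, headed Unscheduled Visits, asks that subjects who leave early have a final visit with the Follow-up Visit examinations. Protocol 4.9.4 asks for the same visit after withdrawal of consent or non-compliance.

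**The concern.** A by-visit safety table is read as a description of subjects at that point in treatment. Day 15 is the end-of-treatment row. Under 7.3.3 it can hold measurements taken after little more than half of the planned doses, from subjects who then left, with nothing in the table to mark them. The Day 8 row can likewise hold an examination made after a single dose. The denominators would then count subjects as examined at a visit they did not attend.

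This matters somewhat more than usual because safety against vehicle is a stated objective, the protocol plans no statistical analysis of safety data, and SAP 7.4.2 plans no safety monitoring committee. The descriptive by-visit tables are a main presentation of vital signs and redness.

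There is also a question of which rule governs. If the exit visit counts as unscheduled, SAP 7.3.1 says to list it only, while SAP 7.3.3 says to tabulate it.

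**Working it through.** **Inputs.** Scheduled clinic visits: Days 1, 8, 15 and 16 (protocol study summary). Tolerance: ±1 day for Days 8 and 15 (protocol 7.2.9). Dosing: evenings from Day 1 to Day 14, "repeat this procedure 13 times for a total of 14 doses" (protocol 6.1). Sample size: 36 completers, about 10% drop-out, 40 randomized 1:1 (protocol 9.1).

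**Reading of the rule.** Distances use nominal visit days. I take the next available visit to be the next later scheduled visit without data. Every randomized subject has Day 1 data, since qualification depends on them. If Day 1 were not counted as a candidate visit, exits on Days 2 to 4 would still go to Day 8, so that result does not depend on this choice.

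**Closest visit.** The midpoint of Days 1 and 8 is (1 + 8)/2 = 4.5, so Days 2 to 4 are closest to Day 1. The midpoint of Days 8 and 15 is (8 + 15)/2 = 11.5, so Days 9 to 11 are closest to Day 8.

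**Doses.** With evening dosing, a morning examination on day *d* follows at most *d* − 1 doses: 7 at Day 8 and 14 at Day 15.

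| Exit day | Day 8 data | Closest visit | Tabulated as | Assigned day minus actual day | Maximum doses |
|---|---|---|---|---|---|
| 2, 3, 4 | none | Day 1 (filled) | Day 8 | 6, 5, 4 | 1, 2, 3 |
| 5, 6 | none | Day 8 | Day 8 | 3, 2 | 4, 5 |
| 7 | none | Day 8 | Day 8 | 1 | 6 |
| 9, 10, 11 | valid | Day 8 (filled) | Day 15 | 6, 5, 4 | 8, 9, 10 |
| 9, 10, 11 | none | Day 8 | Day 8 | −1, −2, −3 | 8, 9, 10 |
| 12, 13 | either | Day 15 | Day 15 | 3, 2 | 11, 12 |
| 14 | either | Day 15 | Day 15 | 1 | 13 |

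A Day 9 exit with valid Day 8 data has had at most 8/14 = 57% of the planned doses when it enters the Day 15 row, although Day 9 lies inside the Day 8 window. The closest-visit step alone also reaches outside ±1 day, for example on Days 5, 6, 12 and 13. Deleting only the second step would therefore not be enough.

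**Size.** The plan's own figure reproduces: 36/(1 − 0.10) = 40. Expected drop-outs are 40 − 36 = 4, or 2 per arm if evenly split. If both in an arm were relabelled to Day 15, they would be 2/(18 + 2) = 10% of that arm's Day 15 row. If all four fell in one arm of 20, the figure would be 4/20 = 20%.

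**The case against.** The strongest reply is that nothing is imputed. Every value was measured on that subject at a real visit, and 7.3.3 only decides which row it goes in. That stands. A reader might infer from "Observed case data will be used; no imputation will be performed for missing safety data" that 7.3.3 contradicts the observed-case rule. The documents do not support that: the rule bars filling in missing values, and 7.3.3 fills in none. What remains is a tension. A by-visit observed-case table implies that the value was observed at that visit, and 7.3.3 is not among the exceptions SAP 10 refers to.

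Second, it would be wrong to say that any Day 9 exit is reported as Day 15. This requires valid Day 8 data. Without them the examination goes to Day 8, one day away and inside the window.

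Third, one might infer that off-drug values dilute the active arm's Day 15 redness. The documents do not show that exit examinations are usually off drug. Protocol 2.2 reports that redness in earlier studies cleared within 8 hours, while dosing at 8PM to 10PM puts the 8AM check 10 to 12 hours later. Little redness may remain then even on treatment. The direction and size of any bias are unknown.

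Fourth, the exit visit may supply little. The Follow-up Visit text in protocol 7.2.6 describes an 8AM visit with heart rate, blood pressure and redness, and lists no biomicroscopy or ophthalmoscopy. The schedule table is not visible, so this cannot be settled.

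Fifth, the conflict with SAP 7.3.1 is possible rather than certain. Protocol 4.9.4 describes the same visit outside the Unscheduled Visits section, and 7.3.3 is the more specific rule. But the SAP does not say which prevails.

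**Conclusion.** The point holds as a visit-labelling fault with limited reach. With valid Day 8 data, exits on Days 9 to 11 enter the Day 15 summaries 4 to 6 days late. Exits on Days 2 to 4 enter the Day 8 summaries equally late. Both fall outside the protocol's ±1 day tolerance for the visit they are assigned to.

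The 10% per arm at Day 15 is a ceiling. It assumes the planned drop-out, an even split, an exit examination in every case, and an exit day that maps to Day 15. Subjects lost to follow-up may have no exit visit, those who leave on Days 2 to 6 go to Day 8, and those who stop drug but stay in the study are not early terminations. The true share is probably smaller.

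The affected output is the descriptive by-visit safety summary, mainly heart rate, blood pressure and redness at the timepoint the exit visit supplies. Adverse event tables are not by visit, and 7.3.3 covers safety variables only, so neither those tables nor the efficacy analyses change. The by-subject listings carry the data in any case.

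**What to change.** In SAP 7.3.3, delete the sentence that sends data to the next available visit, and replace the section with text such as:

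> Early-termination safety data are assigned to a scheduled visit only if the examination falls within that visit's ±1 day window and the visit has no data. All other early-termination safety data are summarised by treatment in a separate row labelled Early termination. The listing gives the number of days since the last dose. For early-exit visits this section takes precedence over Section 7.3.1.

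Add the same cross-reference where SAP 10.3 and 10.4 exclude unscheduled results from the summaries. Make the change before unmasking.

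The cost is one extra row in the by-visit safety tables and slightly smaller Day 8 and Day 15 denominators. No data are lost, and no sample-size figure changes.

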### **7.3.4. Pooling of Investigational Sites**

The data from all study centers will be pooled together for all planned analyses.

### **7.3.5. Coding Conventions for Events and Medications**

All adverse events, and medical history will be mapped to the Medical Dictionary for Regulatory Activities (MedDRA Version 22.0) system for reporting (preferred term and body system).

Prior and Concomitant medications will be coded using WHO-DD (Drug Dictionary) (Version January 2019).

### **7.3.6. Analysis Software**

Data manipulation, tabulation of descriptive statistics, calculation of inferential statistics, and graphical representations will be performed primarily using SAS (release 9.4 or higher) for Windows. If the use of other software is warranted, the final clinical study report will detail what software was used and for what purposes.

### **7.3.7. Study Data**

[figure not shown]
Study data identified in the schedule for time and events ([Table 1](#)) are collected, and source verified, on paper CRFs; there is no electronic data capture tool.

All study data will be formulated into regulatory compliant data sets to provide transparency, traceability, and integrity of trial analysis results from the collection source. Observed study data will be mapped to the Clinical Data Interchange Standards Consortium (CDISC) Study Data Tabulation Model (SDTM) and serve as the source data from the trial. All study analyses will be completed using analysis data sets that are derived from the SDTM and follow the CDISC Analysis Data Model (ADaM) architecture.

The methods for programming the CDISC SDTM and ADaM data sets are described in [Figure 1](#).

**Figure 1 SDTM, ADaM, and TFL Development and Validation**

Where:

1. Development, Validation, and Maintenance of SDTM Domains
2. Development and Validation of ADaM Data Sets, with input source the appropriate SDTM domains.
3. Development and Validation of Tables, Figures, and Listings (TFL), with input data source the SDTM domains and analysis specific ADaM data sets.

#### 7.4. Planned Study Analyses

##### 7.4.1. Statistical Summaries: Descriptive and Inferential

Categories for data presentation and analysis will consist of each treatment group separately: Nyxol or placebo.

All statistical tests will be two-sided and a difference resulting in a p-value of less than or equal to 0.05 will be considered statistically significant. All p-values will be rounded to and displayed in four decimals. If a p-value less than 0.0001 occurs it will be shown in tables as <0.0001.

Descriptive summaries of variables will be provided where appropriate. For continuous variables, the number of non-missing values (n), mean, standard deviation, median, minimum, and maximum will be tabulated by treatment. For categorical variables, the counts and proportions of each value will be tabulated by treatment. Expansion of

descriptive table categories within each treatment may occur if such elaborations are thought to be useful.

All study related data collected will be presented in listings. Study related data not subject to analysis according to this plan will not appear in any tables or graphs but will be included in the data listings.

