9. STATISTICS

9.1. *Sample Size*

A sample size of 36 total completed subjects is needed for the study. Thirty-six completed subjects, who were originally randomized in a 1:1 ratio to the Nyxol 1% and the placebo groups, [REDACTED]

[REDACTED] Additionally, it is assumed that there will be approximately 10% drop-out between Baseline/Day 1 and Day 15. To account for this drop-out, a total of 40 subjects will be randomized into the study.

9.2. *Analysis Populations*

Full Analysis Set (FAS): The FAS will include all randomized subjects who have received at least 11 doses of study medication without missing 2 consecutive doses and have both a Baseline and a Day 15 IOP measurement. This population is also known as the Per Protocol (PP) population. The FAS will be used to analyze efficacy endpoints.

All Randomized Population (AR): The AR population will include all randomized subjects. This population is also known as the intent-to-treat (ITT) population. The AR population will be used in confirmatory efficacy analyses.

Safety Population (SP): The SP will include all randomized subjects who have received at least one dose of study medication. The SP will be used to summarize safety variables.

9.3. *Statistical Methods*

9.3.1. **General Considerations**

All continuous variables will be summarized by treatment and timepoint (as applicable) using descriptive statistics (n, mean, median, standard deviation, minimum, and maximum). All categorical variables will be summarized by treatment and timepoint (as applicable) using frequency counts and percentages.

All study data will be listed by treatment, subject and timepoint (as applicable).

All statistical tests will be performed using a significance level of 5% (two-tailed). Given the large number of secondary efficacy endpoints, the p-values for those analyses will be considered descriptive.

9.3.2. **Demographic and Baseline Characteristics**

Demographic and Baseline characteristics such as age, race, gender, and history of ocular surgery and procedures, will be summarized by treatment group using the FAS and the AR population. These data will also be provided in by-subject listings.

9.3.3. **Subject Disposition**

Subject disposition, including randomization, and completion and withdrawal from the study will be summarized using the AR population. These data will also be provided in by-subject listings.

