#### **3.3. Summary of Statistical Analysis Changes to the Protocol**

The analyses described in this analysis plan are consistent with the analyses described in the study protocol.

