#### **4.2.2. Secondary Endpoints**

Secondary endpoints for efficacy and safety assessments include the following:

Efficacy:

Secondary efficacy endpoints will be analyzed by study eye, fellow eye and all eyes (the pooled data from the study eye and fellow eye) unless otherwise indicated, and will include:

- Change from Baseline to Day 15 in mean diurnal IOP in the fellow eye and all eyes.
- Change from Baseline to Day 8 in mean diurnal IOP.
- Mean IOP at each post-treatment timepoint (8AM, 10AM and 4PM; on Day 8 and Day 15).
- Change and percent change from Baseline to Day 8 and Day 15 in IOP at each timepoint (8AM, 10AM, 4PM), and Day 16 at 8AM.

- Percentage of subjects achieving reductions from Baseline to Day 8 and Day 15 in IOP at 8AM of greater than or equal to 10%, 15%, 20%, 25% and 30%.
- Percentage of subjects achieving Day 8, Day 15 and Day 16 IOP levels at 8AM of less than or equal to 16mmHg, 18mmHg, 20mmHg and 22mmHg.
- Change and percent change from Baseline Day 8, Day 15, and Day 16 in IOP at 8AM.
- Change and percent change to Days 8, 15, and 16 in pupil diameter at 8AM.
- Percentage of subjects achieving reductions from Baseline to Day 8, Day 15 and Day 16 in pupil diameter at 8AM, of greater than or equal to 10%, 15%, 20%, 25%, and 30%.
- Change from Baseline to Day 8, Day 15, and Day 16 in best corrected distance visual acuity (BCDVA) (Early Treatment Diabetic Retinopathy Study [ETDRS] high contrast) (photopic and mesopic) at 8AM.
- Change from Baseline to Day 8, Day 15, and Day 16 in distance corrected near visual acuity (DCNVA) (ETDRS high contrast) (photopic and mesopic) at 8AM.
- Percentage of subjects achieving improvements from Baseline to Day 8, Day 15, and Day 16 in BCDVA and DCNVA (photopic and mesopic) of greater than or equal to 1 line, 2 lines and 3 lines. For BCDVA, only the number of letters read is collected; this will be converted to lines as follows: 1 line = 3-7 letters read; 2 lines = 8-12 letters read; 3 lines = 13-17 letters read, etc. For DCNVA, only the logMAR value is collected; this will be converted to lines as follows: 1 line = 1.3 logMAR; 2 lines = 1.2 logMAR; 3 lines = 1.1 logMAR, etc. to 14 lines = 0.0 logMAR, 15 lines = -0.1 logMAR, 16 lines = -0.2 logMAR, and 17 lines = -0.3 logMAR.

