All secondary endpoints related to IOP will be analyzed additionally in those subpopulations with Baseline IOP of  $<25\text{mmHg}$  and  $\geq 25\text{mmHg}$ . Subjects will be categorized as " $<25\text{mmHg}$ " if their study eye Baseline IOP readings at all time points (8AM, 10AM, and 4PM) are  $<25\text{mmHg}$ .

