#### **7.5. Multiple Testing Procedures**

There will be no adjustments for multiplicity and no formal multiple testing procedures are to be implemented with this analysis plan.

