**Table 2 Clinical Efficacy Assessments**

Efficacy Assessment	Equipment Name	Measurement (Unit)	Procedure
IOP	[REDACTED]	mmHg	[REDACTED]
Distance VA	[REDACTED]	Letters	[REDACTED]
Near VA	[REDACTED]	Jaeger	[REDACTED]

Pupil diameter		mm	

\*For this study photopic and mesopic light conditions are considered to be “with the lights on or with the lights off”.

IOP measurements at the Baseline Visit and both Treatment-study Visits will be performed at 8AM, 10AM and 4PM. All IOP measurements have a window of  $\pm 15$  minutes with at least 2 hours between the 8AM and 10AM assessments. IOP will be measured twice in both eyes at each timepoint. The mean value at each timepoint for the study eye will be used in efficacy assessments. If the difference in the two IOP measurements is  $> 5\text{mmHg}$ , a third measurement will be obtained, and the three values averaged. Mean diurnal IOP is the mean of the IOP measurements at all three timepoints (8AM, 10AM, 4PM).

Near and distance VA and pupil diameter will be performed in photopic and mesopic conditions. Furthermore, near and distance VA will each be assessed using monocular (OD and OS separately) and binocular (OU [both eyes]) measurements.

Primary Efficacy Endpoint:

The primary efficacy endpoint will be analyzed using ANCOVA with change from Baseline to Day 15 in mean diurnal IOP in the study eye as the dependent variable; treatment as a factor; and Baseline mean diurnal IOP as the covariate. The ANCOVA will be performed using the FAS, with subjects included in their randomized treatment group regardless of the treatment they actually received. The least-squares mean (LSM) and standard error (SE) will be provided for both treatment groups, along with the placebo-corrected LSM (Nyxol – placebo), its 95% confidence interval (CI) and associated p-value.

A confirmatory analysis of the primary efficacy endpoint will be performed, using the AR population with missing Day 15 values imputed. See [Section 7.3.2](#) for imputation methods.

Another confirmatory analysis of the primary efficacy endpoint will be performed using the PP population. No imputation of missing Day 15 values will be applied.

Secondary Efficacy Endpoints:

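### The SAP calls any p-value of 0.05 or less statistically significant and omits the protocol's rule that secondary p-values are descriptive

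*SAP*

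**What the plan says.** Protocol 9.3.1 sets a two-tailed 5% level for all tests and then qualifies it: "Given the large number of secondary efficacy endpoints, the p-values for those analyses will be considered descriptive".

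SAP 7.4.1 keeps the level and attaches a label to it. For all tests, two-sided, "a difference resulting in a p-value of less than or equal to 0.05 will be considered statistically significant". The qualification is not repeated there or anywhere else in the published SAP text. SAP 7.5 adds: "There will be no adjustments for multiplicity and no formal multiple testing procedures are to be implemented with this analysis plan".

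SAP 9.1 asks for a p-value from an ANCOVA for each continuous secondary endpoint and from a logistic regression for each responder endpoint. SAP 3.3 declares no departure from the protocol: "The analyses described in this analysis plan are consistent with the analyses described in the study protocol".

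There is one primary efficacy endpoint, the change to Day 15 in study-eye mean diurnal IOP. Its designated primary analysis is an ANCOVA in the FAS.

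**The concern.** The protocol gives two instructions together: test at 5%, but read the secondary p-values as description. The SAP carries over only the first and widens it into a labelling rule for every test. A programmer or report author working from the SAP would mark any secondary result at or below 0.05 as statistically significant, which the protocol rules out.

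The stake is in reporting. SAP 3.2 foresees use of the results in regulatory submissions and manuscripts. The trial plans 36 completers, 18 per arm, and has several responder cut-offs per endpoint, three eye sets and two IOP subgroups. If the primary endpoint failed, chance results carrying that label could be read as positive evidence.

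**Working it through.** **The texts side by side**

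| Point | Protocol 9.3.1 | SAP |
|---|---|---|
| Level | 5%, two-tailed, all tests | 0.05, two-sided, all tests (7.4.1) |
| Label | none stated | statistically significant at or below 0.05 (7.4.1) |
| Secondary p-values | descriptive | nothing said |
| Multiplicity adjustment | none described | none (7.5) |
| Declared change | – | none (3.3) |

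**Number of secondary tests**

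The documents state no number of tests, so there is no plan figure to reproduce. The inputs are the endpoint list in SAP 4.2.2, its three eye sets (study, fellow, all), the two IOP subgroups ("All secondary endpoints related to IOP will be analyzed additionally in those subpopulations with Baseline IOP of" below 25 mmHg and of 25 mmHg or more) and the two light conditions ("Near and distance VA and pupil diameter will be performed in photopic and mesopic conditions", SAP 9.1). The count is for the FAS only. The bullet that repeats the 8AM change in IOP is counted once.

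IOP, per eye set:
- Day 8 diurnal change: 1
- mean IOP: 2 days × 3 times = 6
- change and percent change: (2 × 3 + 1) × 2 = 14
- percent-reduction cut-offs: 2 days × 5 = 10
- IOP-level cut-offs: 3 days × 4 = 12

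The sum is 43. Over three eye sets, plus Day 15 diurnal change in the fellow eye and all eyes, 43 × 3 + 2 = 131. Overall plus two subgroups: 131 × 3 = 393.

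Pupil, per eye set: change and percent change 3 × 2 × 2 = 12; cut-offs 3 × 5 × 2 = 30. Then 42 × 3 = 126.

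Acuity, per eye set: change 2 charts × 3 days × 2 lights = 12; line gains 12 × 3 = 36. Then 48 × 3 = 144.

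Total listed: 393 + 126 + 144 = 663.

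**Removing exact duplicates**

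With Baseline as covariate, an ANCOVA on post-treatment IOP gives the same treatment effect and p-value as an ANCOVA on change from Baseline at that timepoint, because the outcome differs only by the covariate. The mean-IOP tests therefore add nothing new: 6 × 3 eye sets × 3 populations = 54, and 663 − 54 = 609.

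**Expected number at or below 0.05**

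The formula is tests × 0.05. It does not depend on correlation between tests, but it needs every null to be true and every test to have a true size of 5%.

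| Count | Tests | × 0.05 |
|---|---|---|
| Distinct tests, FAS | 609 | 30.5 |
| Without pupil (609 − 126) | 483 | 24.2 |
| Also without Day 16 IOP outside the study eye (483 − 36) | 447 | 22.4 |
| Study eye, no subgroups (43 + 42 + 48 − 6) | 127 | 6.4 |

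Pupil is removed because the protocol's design justification expects a smaller pupil, so a significant pupil result would not be presumed false. Day 16 IOP is removed because Protocol 7.2.6 measures it in the study eye only, although Protocol 4.1 says both eyes at all timepoints. The 36 is (2 + 4) tests × 2 eye sets × 3 populations.

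**How far true sizes depart from 5%**

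Simulation at 18 per arm gave the following.
- A Wald test in a logistic regression rejects about 0% of the time at response rates of 3–5%, 0.2% at 10%, 1.9% at 20% and 5.3% at 40%. Of the 609 tests, 396 are logistic. The Wald form is an assumption.
- A pooled all-eyes ANCOVA that ignores pairing rejects about 12.5% of the time at an assumed between-eye correlation of 0.5, and about 15% at 0.8. SAP 9.1 states no within-subject term.

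The two departures pull in opposite directions, so the counts are illustrative.

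**The case against.** The best defence is that the SAP omits the descriptive rule without revoking it. The protocol itself holds a blanket 5% level and the descriptive rule together without conflict. SAP 7.4.1 could be read as restating the first as a convention, next to its rounding and display rules. SAP 3.3 could be read as leaving the second in force, and SAP 5.1 calls the protocol the definitive reference.

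It stands that this is an omission. A reader might infer that the SAP withdrew the protocol's rule; no sentence does so. But the defence does not remove the conflict. The remark in SAP 5.1 introduces an overview of study design. The statement in SAP 3.3 is not a reliable guide, because the SAP departs elsewhere without saying so: it creates a separate PP population where Protocol 9.2 makes PP another name for the FAS, and it drops percent change in visual acuity from the endpoint list.

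A second objection is that having no multiplicity adjustment is reasonable in a Phase 2 trial with one primary endpoint and descriptive secondary p-values. This stands in full. SAP 7.5 is not a fault in itself; the difficulty arises only when it is combined with the label in 7.4.1.

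A third objection is that the fix changes no p-value. That is also true: the same number would fall at or below 0.05 and be printed. The counts measure how many results are exposed to the label. They do not measure harm already done, and misuse in later reporting is a possibility only.

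**Conclusion.** The point holds as an undeclared inconsistency between SAP and protocol over how secondary p-values are labelled. It should be corrected before unmasking. It does not touch the primary analysis, whose single test keeps its 5% error rate.

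Its size is nominally about 30 secondary results at or below 0.05 out of 609 distinct tests. That drops to about 22–24 under the narrower counts and to about 6 for the study eye without subgroups. These figures rest on a global null, exact 5% size and the FAS alone.

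The documents do not support two stronger readings. A reader who counts every listed test might infer that about 33 false positives are to be expected (663 × 0.05). That counts 54 duplicate p-values, treats an expected pupil effect as null and assumes sizes that sparse logistic tests do not reach. A reader might also infer that the AR and PP analyses of the primary endpoint should be downgraded. Protocol 9.3.1 makes only secondary-endpoint p-values descriptive, and the SAP presents both of these analyses as confirmatory.

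**What to change.** In SAP 7.4.1, limit the term 'statistically significant' to the primary efficacy endpoint, with the FAS ANCOVA as the primary analysis. In SAP 7.5, state that p-values for all secondary efficacy endpoints, including the fellow-eye, all-eyes and IOP-subgroup analyses, are nominal and descriptive, as in Protocol 9.3.1. Leave the AR and PP analyses of the primary endpoint in the supportive, confirmatory role the SAP gives them.

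If the sponsor does intend significance claims on secondary endpoints, the alternative is to declare that change in SAP 3.3 and add a multiplicity procedure.

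The cost is two sentences before unmasking. No analysis or table changes. Secondary results could no longer be called significant, which the protocol already accepts.
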